## 14.6 Biomarker Evaluation

The following analysis will be performed to investigate the relationship between endpoints and biomarker levels (e.g. STAT3, phospho-STAT3,  $\beta$ -catenin):

For each biomarker, Cox Proportional Hazards model will be used to model the relationship between Overall Survival, Progression-Free Survival and duration of response with baseline value of the biomarker. The model will also include assigned treatment, interaction between treatment and biomarker, and will be stratified by baseline ECOG performance status.

For biomarkers with post-baseline measurements, similar analysis will be done with change from baseline of a biomarker as a covariate, for each of the time points. An additional model that includes prognostic factors may be investigated.

The relationship between the endpoint and binary biomarkers (e.g. baseline phospho-STAT3 status,  $\beta$ -catenin) will be also examined using the log-rank test, stratified by treatment and baseline ECOG performance status. Subgroup analysis by the status of the binary biomarker may also be performed. The Kaplan-Meier method will be used to describe overall survival, progression-free survival and duration of response by the status of the biomarker (e.g. phospho-STAT3-high vs. phospho-STAT3-low) and by treatment group.

The relationships between the binary response variable (e.g. objective response, DCR) with baseline values of biomarkers as well as with their change from baseline at different time points will be investigated using logistic regression that includes assigned treatment, biomarker value and treatment-by-biomarker interaction, stratified by baseline ECOG performance status. Additional model that includes prognostic factors may be investigated. Relationship between the response and binary biomarkers (e.g. baseline phospho-STAT3 status or STAT3 status) will also be examined using the CMH test, stratified by treatment and baseline ECOG performance status. Subgroup analysis by the status of the binary biomarker may also be performed.

Exploratory analyses, additional to those described in this section, such as alternative modeling approaches and analyses of other biomarkers are expected and may be performed. All analyses described in this section are based on availability of data.

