- To explore associations with baseline values and changes of putative biomarkers (see Appendix VI) in the blood and the potential for clinical benefit in terms of overall survival, progression-free survival, disease control rate, and objective response rate, from treatment with BBI608 in patients with pre-treated advanced colorectal carcinoma.
- To establish a comprehensive tumour bank linked to a clinical database for the further study of molecular markers in colorectal cancer.

AMEND #3: 2014-OCT-01

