# 9.1 Evaluation During Protocol Treatment

	Investigations	Timing from Randomization	
Physical Examination	
 
Physical examination
 
Vital signs
 
Weight + ECOG Performance status
 
		
Hematology  • CBC + differential, Platelet count  • Creatinine, Total Bilirubin, ALT, Alkaline Phosphatase, LDH, Albumin, Potassium, Magnesium, Phosphate  • CBC + differential, Platelet count			
		Every 4 weeks (every 28 days) after	
Urinalysis	Dipstick (including protein, specific gravity, glucose and blood)	randomization 	
Economics	Resource Utilization Assessment		
Other Investigations	• Serum or urine pregnancy test 		
Other Investigations	Serum CEA		
	• Adverse Event evaluation must be done at each study visit for the preceding 4 week reporting period 		
Adverse Events 	• Adverse Event evaluation by phone to assess tolerability of dosing regimen 	Within 24-48 hrs of start of protocol treatment, and at 2 weeks (approximately 14 days) and 6 weeks (approximately 42 days) after randomization	
Cardiology Assessment	• ECG	2 hours after first dose on first day of treatment and as clinically indicated thereafter	
Radiology & Imaging	CT/MRI scan as per baseline assessment with tumour measurement and evaluation by RECIST 1.1 criteria 	Every 8 weeks (every 56 days) after randomization 	
Correlative Studies & Tissue Banking	
 
Submission of whole blood sample to central tumour bank 
 
	At 4, 8 and 12 weeks after randomization 	
Sparse PK Collection	• Submission of blood plasma samples to central lab 	At 4, 8 and 12 weeks after randomization 	
Quality of Life	• EORTC QLQ-C30 	At 4, 8, 12, 16 and 24 weeks after	
Health Utilities	• Health Utilities Index (HUI3) 6	randomization	

 Patients are to be assessed every 4 weeks (28 days) while on study medication and until the first regularly scheduled 4 week assessment at which the patient has been off study therapy for a minimum of 28 days.

In women of childbearing potential only a negative pregnancy test must be demonstrated every 4 weeks until 4 weeks after the administration of the final dose of protocol therapy. The minimum sensitivity of the pregnancy test must be 25 IU/L or equivalent units of HCG.

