#### 9.2 Evaluation After Protocol Treatment Discontinuation

Investigations		Timing from Randomization	
Physical Examination	
 
Physical examination
 
Vital signs
 
Weight + ECOG Performance status
 
	Every 4 weeks (every 28 days) after randomization until the first regularly scheduled 4 week	
Economics	Resource Utilization Assessment	assessment at which the patient has been off study therapy for a minimum of 28 days, and every 8	
Adverse Events 	* Adverse Event evaluation must be done at each study visit for the preceding reporting period 	weeks (56 days) thereafter until deterioration to ECOG PS 4 or hospitalization for end of life care.	
Overall Survival	• Assess for survival of patient 	Every 4 weeks (every 28 days) after randomization until the first regularly scheduled 4 week assessment at which the patient has been off study therapy for a minimum of 28 days, and every 8 weeks (56 days) thereafter.	
Other	• Serum or urine pregnancy test 		
Investigations	Serum CEA		
Hematology	CBC + differential, Platelet count	Every 4 weeks (every 28 days) after randomization	
Biochemistry	Creatinine, Total Bilirubin, ALT,     Alkaline Phosphatase, LDH, Albumin,     Potassium, Magnesium, Phosphate	until the first regularly scheduled 4 week assessment at which the patient has been off stud therapy for a minimum of 28 days	
Urinalysis	Dipstick (including protein, specific gravity, glucose and blood)		
Cardiology Assessment	• ECG	At the first regularly scheduled 4 week assessment at which the patient has been off study therapy for a minimum of 28 days	
Radiology & Imaging	• CT/MRI scan as per baseline assessment with tumour measurement and evaluation by RECIST 1.1 criteria 	Every 8 weeks (56 days) after randomization until objective disease progression is documented 	
Correlative Studies & Tissue Banking	• Submission of whole blood sample to central tumour bank 	At 4, 8 and 12 weeks after randomization 	
Quality of Life	• EORTC QLQ-C30 	At 4, 8, 12, 16 and 24 weeks after randomization or	
Health Utilities	• Health Utilities Index (HUI3) 6	until deterioration to ECOG PS 4 or hospitalization for end of life care 	

 Adverse events will be recorded and graded according to the NCI Common Terminology Criteria for Adverse Events (see Appendix V).

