## **Progression-Free Survival**

Progression-Free Survival (PFS) is defined as the time from randomization to the first objective documentation of disease progression or death due to any cause. If a patient has not progressed or died at the time of final analysis, PFS will be censored on the date of the last tumour assessment. This includes patients who are lost to follow-up or have withdrawn consent. All analyses for OS will also be performed for PFS, using similar methodology.

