Using data from this and other trials, the relationship between a number of molecular markers associated with the STAT3,  $\beta$ -catenin and other related pathways, and the clinical outcomes of BBI608 therapy will be explored. Multiple molecular markers in a paraffin-embedded tumour tissue sample can be determined by analyzing RNA and protein in the tissue sample.

In addition to analysis of potential biomarkers of benefit from BBI608 therapy, an analysis of markers of resistance to BBI608 will be conducted using serial plasma samples which will be drawn at baseline as well at 4, 8 and 12 weeks post initiation of therapy. This analysis may involve SNPs, CYPS, and metabolomics.

Paraffin-embedded tumour specimens, or cores (two 2 mm cores of tumour from the block) and unstained slides obtained from paraffin embedded specimens will be required for the patient to be enrolled on the trial. The patient must consent to provision of, and investigator(s) must confirm access to and agree to submit at the request of the NCIC CTG Central Tumour Bank, a representative formalin fixed paraffin block of tumour tissue in order that the correlative studies may be conducted.

Blood samples will be collected prior to dosing with BBI608 and then at weeks 4, 8 and 12 during BBI608 therapy.

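### Week-8 and week-12 blood-marker changes can enter the PFS, DCR and response models after the outcome they are meant to explain has already occurred

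*Protocol*

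**What the plan says.** Section 14.6 sets out Cox models to "model the relationship between Overall Survival, Progression-Free Survival and duration of response with baseline value of the biomarker", with assigned treatment and the treatment-by-marker interaction, stratified by ECOG status. For markers with post-baseline values, "similar analysis will be done with change from baseline of a biomarker as a covariate, for each of the time points". For objective response and DCR, the relationship with baseline values "as well as with their change from baseline at different time points will be investigated using logistic regression", again with the interaction. The section names no landmark, no time-dependent covariate and no restriction to patients still event-free when the sample is drawn. It closes by allowing exploratory analyses in addition to these.

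The timing comes from other sections:

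- **Samples.** Section 9.1 schedules correlative blood at weeks 4, 8 and 12. Section 9.2 keeps the same schedule after treatment has stopped: "At 4, 8 and 12 weeks after randomization". Appendix VI describes "serial plasma samples which will be drawn at baseline as well at 4, 8 and 12 weeks post initiation of therapy" for the study of resistance.
- **Scans.** Section 9.1 schedules imaging "Every 8 weeks (every 56 days) after" randomization, so the first scheduled scan is at week 8.
- **Clocks.** In Section 14.2, "Progression-Free Survival (PFS) is defined as the time from randomization to the first objective documentation of disease progression or death due to any cause". Best response is counted from the start of study treatment (10.2.5), and response duration from the date CR or PR is first met (10.3).
- **Purpose.** A listed objective in Section 1.2 is "To explore associations with baseline values and changes of putative biomarkers (see Appendix VI) in the blood", against OS, PFS, DCR and objective response.

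**The concern.** A covariate in an ordinary Cox or logistic model is treated as known when follow-up starts. A week-12 change is not. If a patient progressed at the week-8 scan, the PFS time is already fixed and disease control is normally settled. Blood drawn four weeks later may then reflect the progression rather than foreshadow it.

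Appendix VI sets out to find blood and tumour markers of benefit from, and resistance to, BBI608. A blood marker that merely moves once the tumour has grown could be read as a marker of resistance, or its absence as a marker of benefit.

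**Working it through.** **1. Order of events**

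| Sample | Scheduled scans by then | Consequence |
|---|---|---|
| Week 4 | none | Only deaths and unscheduled progressions come first |
| Week 8 | week-8 scan, same nominal visit | Documented progression can coincide with or precede the sample |
| Week 12 | week-8 scan, four weeks earlier | PFS or DCR can already be settled |

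Table 1 in Section 10.2.5 accepts stable disease documented once at 5 weeks or more from baseline, so the week-8 scan alone can settle disease control. Section 12.2 lets treatment continue past progression and Section 9.2 keeps sampling after treatment stops, so a sample after the event is an expected occurrence.

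**2. Survival inputs**

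The protocol gives no figure for this analysis. Its design survival inputs, used in step 4, are sound. Section 14.3 states 615 events for HR 0.77, 90% power and two-sided 5%. The Schoenfeld formula gives 4 × (1.960 + 1.282)² / (ln 0.77)² ≈ 616.

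**3. Progression by each sample**

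The QoL part of Section 14.2 gives 8-12 weeks as the approximate mean time to progression in the control arms of two earlier trials. Assuming exponential times, the fraction progressed by week w is 1 − exp(−w/mean):

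- week 8: 1 − exp(−8/12) = 49% to 1 − exp(−8/8) = 63%;
- week 12: 1 − exp(−12/12) = 63% to 1 − exp(−12/8) = 78%.

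Read as a median instead, 8-12 weeks gives 37-50% and 50-65%. Section 14.5 points the same way: an expected placebo DCR of 10-15% leaves 85-90% of placebo patients without disease control, although that group also includes early deaths and unassessed patients.

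**4. Deaths by each sample**

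With medians of 4.6 and 6.0 months and exponential survival, 12 weeks is 12 × 7/30.4375 = 2.76 months. Deaths by then are 1 − exp(−ln 2 × 2.76/4.6) = 34% on placebo and 27% on BBI608. At week 8 they are 24% and 19%. These patients have no sample, so for OS no death precedes its own marker. A Cox fit for OS in patients with a sample is in effect an analysis of those alive at the sample.

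**5. Illustration of the bias for PFS**

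The simulation used 217 patients at control-like rates: mean time to progression 10 weeks, median OS 4.6 months, and progression documented at the next 8-weekly scan. Everyone alive at the sampling week had a sample. The marker had no effect on outcome but shifted once PFS had ended. There were 200 runs per setting.

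| Sample | Shift | HR per SD, model as written | Nominally significant | Landmark HR |
|---|---|---|---|---|
| Week 4 | 1 SD | 1.00 | 1% | 1.00 |
| Week 8 | 0.5 SD | 1.13 | 28% | 1.00 |
| Week 8 | 1 SD | 1.25 | 94% | 1.00 |
| Week 12 | 0.5 SD | 1.14 | 26% | 0.99 |
| Week 12 | 1 SD | 1.25 | 89% | 1.00 |

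With no shift, the model as written was nominally significant in at most 1% of runs. About 55% of patients with a week-8 or week-12 sample had already had their PFS event. The week-8 rows assume that a sample at the progression visit already shows the shift. The landmark sets held about 189, 74 and 65 patients at weeks 4, 8 and 12.

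**The case against.** The strongest reply is that this is exploratory work whose details belong in a statistical analysis plan. Section 14.6 asks only for a similar analysis and expects alternative modelling. That does not fully answer the point. The protocol names the model and the covariate, and the alternatives are additional to it.

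It is also fair that Appendix VI describes the on-study samples as drawn during therapy, which sits uneasily with Section 9.2. Because treatment may continue past progression, that reading reduces the problem without removing it.

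Several stronger readings are tempting, and the documents do not support them:

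- *All three weeks are equally affected.* Week 4 precedes every scheduled scan, and week 8 coincides with the first.
- *OS has the same error.* Patients who die early have no later sample, so the issue for OS is selection of survivors and labelling.
- *49-63% and 63-78% are the shares of modelled patients with a sample taken after the event.* They are shares of control patients progressing on a continuous curve. Documentation follows the scans, and patients who died or gave no sample drop out.
- *An HR of 1.25 is the expected bias.* It follows from an assumed 1 SD shift. At 0.5 SD the effect is about half as large.
- *The biomarker-positive analysis is compromised.* Phospho-STAT3 and β-catenin by immunohistochemistry are measured on archival tissue, and Section 14.7 uses that baseline value.

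**Conclusion.** The point holds for blood-marker changes in the models of PFS, objective response, DCR and duration of response. It is clear for the week-12 change, can arise at week 8, and is minor at week 4. The ordering problem does not require every clock to start at randomization: best response and response duration start elsewhere, yet a marker can still be drawn after the response or progression it is related to.

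The fractions progressed by weeks 8 and 12 rest on exponential times and on a mean borrowed from earlier trials. The size of the bias rests on how far a marker shifts after progression, which the documents do not give, so the simulated hazard ratios are illustrations only. The primary OS comparison does not depend on these models. The correction is worth making because the affected analyses serve a listed objective and could mislabel a consequence of progression as resistance or benefit.

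**What to change.** Amend Section 14.6 for markers with post-baseline values:

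- **PFS:** use a landmark at each sampling date, including only patients alive and progression-free then and restarting the clock there, or enter the marker as a time-dependent covariate.
- **Duration of response:** apply the same rule, or use only samples drawn before response onset.
- **Objective response and DCR:** use only changes drawn before the assessment that determines the outcome, for example the week-4 change for week-8 disease control. Drop the week-12 change as a predictor of week-8 disease control. Limiting DCR to later scans instead would redefine the endpoint, so that route is not advised.
- **OS:** label the model as an analysis among patients alive at the sample, with the clock starting there.
- **Interaction:** report the treatment-by-change term as exploratory. It stays conditioned on a post-randomization value under any of these options.

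This needs new wording but no new data. The real cost is numbers: in the simulation the landmark sets fell to about 74/217 = 34% at week 8 and 65/217 = 30% at week 12 under control-like rates.

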Baseline phospho-STAT3 expression by IHC has been reported to correlate with clinical outcome [Morikawa 2011]. These authors evaluated a bank of 724 archival colorectal tumour tissue samples and defined high phospho-STAT3 expression in 18%, low expression in 34%, and no expression in 48%. Cancer-specific and overall survival was higher in those with absent phospho-STAT3 staining (Figure 1).

STAT3 is closely linked to another important oncogene, β-catenin. β-catenin contributes to tumorigenesis and metastasis in a range of cancers and is notable in colorectal cancer for promoting tumorigenesis as a result of APC mutation [Morin 2007]. In addition to its over-expression, β-catenin localization has important clinical implications. Membranous β-catenin is involved in maintaining cell-cell junctions and promoting a less-aggressive epithelial phenotype. By contrast, nuclear β-catenin is associated with the CSC-promoting and metastasis-promoting epithelial-to-mesenchymal transition (EMT) and is present in cells at the invasive front of colorectal tumours [Brabletz 2005, Kawada 2006]. STAT3 and β-catenin reciprocally regulate each other's expression; furthermore, STAT3 activation causes β-catenin to accumulate in the nuclei of colorectal cancer cells. This accumulation contributes to increased CSC abundance and consequently worse prognosis for a subset of colorectal cancer patients [Kawada 2006] (Figure 2). In CRC, there is a significant correlation between archival tissue staining positive for phospho-STAT3 and for nuclear β-catenin by immunohistochemistry (IHC) (92.5%, p<0.01) [Kawada 2006]. Approximately 60-70% of CRC patients are expected to have nuclear localization of β-catenin on IHC of archival tissue [Aamodt 2010, Kawada 2006].

In this study, archival tumour phospho-STAT3 and  $\beta$ -catenin localization will be correlated with clinical outcome to confirm these proteins as prognostic factors, but also to analyze whether phospho-STAT3 and  $\beta$ -catenin expression are biomarkers of benefit from BBI608 therapy.

AMEND #2: 2014-FEB-24

Figure 1 – Correlation of phospho-STAT3 expression with survival in patients with colorectal cancer, from Morikawa *et al.* 

[figure not shown]
[figure not shown]

Figure 2 – Correlation of  $\beta$ -catenin expression with overall survival in patients with colorectal cancer, from Kawada *et al.* 

AMEND #2: 2014-FEB-24

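### The change-from-baseline biomarker models in Protocol section 14.6 omit the marker's own baseline level, so any prognostic effect of that level leaks into the change coefficient

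*Protocol*

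**What the plan says.** Section 1.2 lists among the secondary objectives: "To explore associations with baseline values and changes of putative biomarkers (see Appendix VI) in the blood" and the potential for clinical benefit from BBI608. Appendix VI provides for "serial plasma samples which will be drawn at baseline as well at 4, 8 and 12 weeks post initiation of therapy".

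Section 14.6 gives the models. For overall survival, progression-free survival and duration of response, a Cox model is first fitted on the baseline marker value: "The model will also include assigned treatment, interaction between treatment and biomarker, and will be stratified by baseline ECOG performance status". For markers measured again later, "similar analysis will be done with change from baseline of a biomarker as a covariate, for each of the time points". For objective response and disease control the plan is "logistic regression that includes assigned treatment, biomarker value and treatment-by-biomarker interaction, stratified by baseline ECOG performance status", applied to baseline values and to changes.

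On the natural reading, change takes the place of the baseline value, and no change model names both. Two sentences leave room for more. One is "An additional model that includes prognostic factors may be investigated", which is optional and names no factor. The other says that further exploratory analyses, "such as alternative modeling approaches and analyses of other biomarkers are expected and may be performed".

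**The concern.** Change is follow-up minus baseline, so a patient who starts high tends to fall and one who starts low tends to rise, even when nothing biological has happened. If the starting level itself carries prognosis, a model containing change alone gives part of that prognosis to the change, with the sign reversed. For example, if a high level is adverse, patients with large falls are disproportionately those who started high, and a meaningless fall can look harmful. A fall that truly helps can be hidden. If a high level is favourable, a true adverse effect of a rise is exaggerated.

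This is separate from the timing of the sample: it remains when every patient is followed only from the sampling date. At stake is whether the reported association of marker change with outcome can be told apart from the association with starting level.

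**Working it through.** **Inputs from the protocol.** 1:1 allocation; the model terms quoted above; 195 deaths among 217 ITT-March patients, two-sided 0.05 (section 14.5). Section 14.6 states no figure of its own. As a check on the event basis, Schoenfeld's formula, power = Φ(√(195/4)·|ln HR| − 1.96), gives Φ(2.490 − 1.96) = 70.2% at HR 0.70 (stated 70%) and Φ(1.825 − 1.96) = 44.6% at HR 0.77 (stated 43%).

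**Assumptions, not in the protocol.** Baseline HR per SD of 1.0 to 1.5 as the main range; baseline to follow-up correlation ρ of 0.5 to 0.8; equal SDs at the two times. The simulations quoted without other detail use 190 patients with a later sample and 90% deaths (171).

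**Step 1: the shift.** Let baseline B and follow-up F have unit variance and correlation ρ, and let C = F − B. Then Var(C) = 2(1 − ρ) and Cov(B, C) = ρ − 1, so E[B | C] = −C/2 whatever ρ is. If the log hazard is b·B + c·C, the model with change alone estimates approximately c − b/2.

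**Step 2: false positives when c = 0.** Without the interaction, z = (b/2)·√(D·2(1 − ρ)) with D deaths. With the interaction, the change term is the slope in the reference arm, so D is halved. With D = 171:

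- HR 1.3 (b/2 = 0.131), ρ = 0.8: z = 1.08, 19% without the interaction; z = 0.77, 12% with it.
- HR 1.5 (b/2 = 0.203), ρ = 0.5: z = 2.65, 76% without; z = 1.88, 47% with.
- HR 1.0: 5% in either model.

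Cox simulation over the same range gives 18-69% without the interaction and 12-41% with it. The formula runs somewhat high at the stronger effect. With the baseline level added, rejection is 4-6%. At the protocol's 195 deaths, a weak baseline effect (HR 1.1) gives only 6-12% by the formula without the interaction, as ρ goes from 0.9 down to 0.3.

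**Step 3: a real effect of change.** Take a true HR of 1.3 per unit of change (log HR 0.262), ρ = 0.5, 217 patients and 195 deaths, model without the interaction. Estimate and power with baseline omitted:

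- baseline HR 1.0: 0.261, 93%
- baseline HR 1.3: 0.134, 46%
- baseline HR 1.5: 0.054, 11%
- baseline HR 1.69: 0.003, 3%
- baseline HR 0.77: 0.380, 99.8%

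With baseline included, the estimate is 0.26 to 0.28 and power about 85-88% throughout.

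**Step 4: the treatment-by-change test.** The shift in each arm is minus half that arm's baseline effect, so the interaction shifts by (b_placebo − b_BBI608)/2. With equal effects this is zero, and simulated size with baseline omitted is 5-7%. With baseline HR 1.5 on placebo and 1.0 on BBI608, the shift is 0.405/2 = 0.203. Its standard error is √(4/(171·2(1 − ρ))): 0.153 at ρ = 0.5 and 0.242 at ρ = 0.8. So z = 1.33 and 0.84, or 26% and 13% rejection. Simulation gives 12-21%. Adding only the baseline main effect leaves 12-23%, because one common baseline slope cannot fit two arms. Adding treatment-by-baseline as well gives 5-7%.

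**Step 5: price of the extra term.** Var(C | B) = 1 − ρ². If baseline is not prognostic, including it therefore inflates the standard error of change by √(2/(1 + ρ)): 1.15 at ρ = 0.5 and 1.05 at ρ = 0.8. In Step 3 at baseline HR 1.0, power goes from 93% to 87%.

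**The case against.** The strongest reply is that every figure above for the plan's own model rests on a prognostic baseline level that the protocol does not document for the markers concerned. Appendix VI does state "Baseline phospho-STAT3 expression by IHC has been reported to correlate with clinical outcome", but that is archival tumour tissue, whereas the repeated samples are blood. This stands. A reader might infer that the plan will produce false positives far above 5% and will nearly erase a true effect. The documents do not support either as an unconditional statement. With a non-prognostic baseline, size is 5% and nothing is lost. Near-erasure needs b close to 2c with the same sign; with b = c the effect is halved, and with opposite signs it is exaggerated.

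Second, the objective concerns benefit from BBI608, for which the relevant term is treatment-by-change, and that test keeps its size when the baseline effect is the same in both arms. This also stands, so one cannot conclude that the trial would misjudge the marker as a predictor. The protection depends on equal baseline effects, though. Section 14.6 itself fits treatment-by-baseline interactions, and Appendix VI looks for markers of benefit, so unequal effects are part of what is being studied.

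Third, the work is exploratory, other models are allowed, the baseline-value model is reported alongside, and covariate detail may be left to a statistical analysis plan. This lowers the priority. It does not settle the point, because the protocol lists the terms of these models and an optional model with unnamed factors does not correct them. The baseline level is not expressly excluded, so a clarification would be enough.

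**Conclusion.** The point holds in conditional form. As specified, the change models cannot separate a marker's change from its starting level; the change coefficient is shifted by about -b/2 when SDs are equal. For assumed baseline HRs of 1.3-1.5 per SD and correlations of 0.5-0.8, a null change is declared significant in about 12-41% of trials with the interaction in the model and 18-69% without it, against about 5% with baseline included. There is no inflation if baseline is not prognostic. The treatment-by-change test is sound when the baseline effect is equal across arms, but rejects in about 12-21% of trials if the baseline HR is 1.5 on placebo and 1.0 on BBI608. The algebra is certain; the HRs, correlations and equal SDs are assumptions. The figures are for Cox models of survival. The logistic models omit the same term, but the size there was not calculated. Priority is low, because no decision rule or primary endpoint depends on these analyses.

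**What to change.** In section 14.6, state that every model containing change from baseline of a biomarker (Cox and logistic, at each time point) also includes the baseline value of that biomarker and, wherever treatment-by-change is fitted, the treatment-by-baseline interaction. The baseline main effect alone is not enough to protect the interaction test.

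The cost is one or two extra terms per model. The baseline value is already needed to compute the change, so no data are added. There is a small loss of precision when baseline is not prognostic.
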